## 1.2 Non-specific effects of BCG

Several observational studies in Africa and other high-mortality areas show that BCG is associated with better child survival, which cannot be explained by prevention of tuberculosis (TB).

WHO recommends BCG vaccine at birth to normal-birth-weight children (NBW) in low-income

countries to prevent TB. For low-birth-weight children (LBW;<2500g) BCG vaccination is often delayed because these children are assumed to be immunologically immature, and therefore they are typically only vaccinated when they have reached 2500g. However, in two RCTs in Guinea-Bissau, BCG-at-birth reduced neonatal mortality in LBW children by 48% (95%CI: 18-67%). TB is very rare in early childhood and these strong beneficial effects can therefore not be ascribed to prevention of TB. Rather the effect is due to a beneficial training of the immune system, preventing or ameliorating other infections, which cause neonatal and childhood death. The effect of BCG-at-birth on neonatal mortality was seen already during the first three days post-vaccination, the reduction in mortality being 58% (8-81%). This rapid effect suggests that the effect is due to changes in the innate immune system rather than the adaptive immune system.

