### 5.4.2 Intervention

For all children, the nurse will examine and weigh the child, encourage skin-to-skin contact to keep the new-born warm and if necessary perform umbilical cord care. For children in the control clusters, the nurse will inform about vaccination opportunities (vaccination at closest health centre or vaccination by BHP nurse at next visit), as recommended by WHO. For children in the intervention clusters, the nurse will inform the parents that it is recommended to administer BCG and OPV at birth. If parents accept vaccination, the nurse will administer BCG and OPV, opening a vial of BCG even if there is just one child to be vaccinated (Table 1). Children in the intervention group will be vaccinated with BCG and OPV within 72 hours after birth.

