Appendix 1: General analysis principles

1 Participant population

All main analyses will be completed in a per-protocol (PP) population of all BCG-unvaccinated children, who received a home visit within 72 hours after birth, and who received the assigned treatment. The primary analysis and hence the main conclusion of the trial will be based on the PP analysis. Unless explicitly stated all analyses will be PP.

Since the cluster-size varies, data will be analysed on individual level data. All statistical tests will be 2-tailed and $p \leq 0.05$ considered statistically significant for analyses involving the primary outcome.

2 Unadjusted and adjusted analyses

Both unadjusted analyses and analyses adjusted for place of delivery will be reported. Conclusions will be based on the unadjusted analyses.

3 Multiple testing

P-values will not be corrected for multiple testing. Secondary outcomes are tested to observe if the pattern is similar across other health outcomes. Consequently, $p \leq 0.05$ will not be employed as a threshold for statistical significance for secondary outcomes. For the sensitivity analyses, we will not consider statistical significance, but rather robustness of the conclusions across different definitions of outcomes and co-variates.

4 Missing data

All analyses will be complete-case analyses.

5 Proportional hazards

To test the proportional hazards assumption, a required assumption of the Cox regression, we will perform formal significance tests based on Schoenfeld residuals. In addition, we will assess proportionality by allowing the hazard ratio to interact with the underlying timescale to identify a possible time trend. Finally, we will assess proportionality graphically via log-log survival curves.

Significance tests based on Schoenfeld residuals will be performed via the stata command *estat phtest, detail* leading to both a global test and a test for each covariate, the latter being relevant only when we study effect modifications. Presentation of log-log survival curves will be undertaken via *stphplot*. Finally, possible interactions between hazard ratios and the underlying time scale will be

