Appendix 2 - Planned analyses

1 Baseline

Descriptive statistics:

For eligible children visited by a study nurse within 72 hours after birth, we will describe reasons for exclusion by group allocation.

Distribution of background factors will be presented by group allocation overall and by sex and region. Background factors will be summarised by counts (percentages), means (standard deviation) or medians (interquartile range) as appropriate. Information on the proportion with missing information will be provided.

Table 1: Summary of background factors by intervention and control group

• Sex• Age at enrolment• Region• Weight at enrolment• Temperature• Mid-upper-arm circumference• Head circumference• Place of birth• Socioeconomic factors (maternal education and housing conditions)

2 Primary analysis of primary outcome

The primary analysis of early infant non-accidental mortality will be assessed on a per-protocol (PP) analysis allowing for different baseline hazards according to factors used in the randomization (Region, pre-study mortality level (high/low)) and sex, thus allowing different baseline hazards for boys and girls. To account for clustering we will employ cluster-robust variance estimates.

For the primary outcome, we will use Cox proportional hazards models that allow different baseline hazards according to the above mentioned factors and with age as underlying time-scale. Deaths due to accidents will be censored.

The primary analysis of the primary outcome is described in more detail in table 2.

Table 2: Primary analysis of primary outcome

Population	Children visited within 72 hours after birth are eligible for the study. Exclusion criteria:
------------	---

	
 - Children already BCG vaccinated - Moribund children (Expected not to survive the next 24 hours, as evaluated by the health facility nurse at the enrolment visit) - Children in rural villages where the BHP mobile teams coincidentally were in the village the same day (and vaccinated all children)
Observation period	
From: Enrolment visit or 24 hours after birth, whichever comes last
 
To: 60 days of life
 
Censoring, first of:
 
 - Visit by the BHP - 60 days - Death due to accident - Date of registering first non-trial vaccine given after enrolment - Migration (migration out of the study area as per HDSS definition)
Time scale	Age
Failure definition	Death

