Reasoning	A recent randomized trial in Denmark found that the effect of BCG varied by whether the mother had received BCG or not ³ . Since, BCG scar is a life-long marker of a successful BCG-vaccination, we will assess whether the effect of BCG differs by maternal BCG-scar status
Outline stata code: For analysis:	<pre>stcox random#mBCGscar mBCGscar, strata(sex reg pmorlev) vce(cl regam)</pre>

For model checking:	<pre>contrast random#mBCGscar</pre> <pre>estat phtest, detail†</pre> <pre>stphplot, strata(random_mBCGscar) adj(sex reg prmorlev)</pre> <pre>stcox random#mBCGscar mBCGscar, strata(sex reg prmorlev) ///</pre> <pre>vce(cl regam) tvc(random#mBCGscar mBCGscar) texp(_t)</pre> 
* mBCGscar= maternal BCG scar, reg=region, prmorlev=pre-study mortality level, regam=village cluster, random_mBCGscar=a four-level variable based on the four possible combinations of random and maternal BCG scar

---------------------	--

† If the proportional hazards assumption is not fulfilled we will still report the marginal hazard ratio but it will be supplemented by hazard ratios for two-three categorized time periods.

Table 5. Low birthweight as a potential effect modifier of the primary outcome

Potential effect modifier	Low birthweight (<2500g: yes/no)
Design	We will perform the analysis as described above (for the primary analysis) allowing the effect of the intervention to differ by birthweight strata
Reasoning	Birthweight is an important risk factor for mortality. Previous randomised trials from Guinea-Bissau assessing the effect of BCG on mortality have been performed among low-birth-weight children.
Outline stata code: For analysis: For model checking:	<pre>stcox random#LBW LBW, strata(sex reg prmorlev) vce(cl regam)</pre> <pre>contrast random#LBW</pre> <pre>estat phtest, detail†</pre> <pre>stphplot, strata(random_LBW) adj(sex reg prmorlev)</pre> <pre>stcox random#LBW LBW, strata(sex reg prmorlev) vce(cl regam) ///</pre> <pre>tvc(random#LBW LBW) texp(_t)</pre> 
* LBW=Low birthweight, reg=region, prmorlev=pre-study mortality level, regam=village cluster, random_LBW=a four-level variable based on the four possible combinations of random and low birthweight

† If the proportional hazards assumption is not fulfilled we will still report the marginal hazard ratio but it will be supplemented by hazard ratios for two-three categorized time periods.

Table 6. Season as a potential effect modifier of the primary outcome

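### The mortality model that carries the conclusion has no term for weight at enrolment, although every child is weighed and the SAP calls birthweight an important risk factor

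*SAP*

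**What the plan says.** SAP Appendix 1, section 2 plans two versions of each analysis: "Both unadjusted analyses and analyses adjusted for place of delivery will be reported". It then settles which one counts: "Conclusions will be based on the unadjusted analyses". Section 1 of the same appendix fixes the population: "The primary analysis and hence the main conclusion of the trial will be based on the PP analysis". That population is made up of BCG-unvaccinated children "who received a home visit within 72 hours after birth, and who received the assigned treatment".

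In SAP Appendix 2, Table 2, the primary model is a Cox model with separate baseline hazards by sex, region and pre-study mortality level and cluster-robust standard errors. Treatment is its only covariate. The composite in Table 8 has the same structure.

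Weight appears elsewhere in the plan:

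- Protocol 5.4.2 has the nurse weigh every child, in both arms.
- SAP Appendix 2, Table 1 lists "Weight at enrolment" as a background factor, for description.
- SAP Table 5 gives the reason for studying low birthweight as an effect modifier: "Birthweight is an important risk factor for mortality".
- SAP Table 11 uses weight-for-age at enrolment as a covariate, but for the growth outcome only.

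No overall weight-adjusted hazard ratio is planned for death or for the composite.

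**The concern.** In a comparison of everyone randomised, a pre-specified analysis without prognostic covariates is valid, and leaving weight out costs only some precision. Here membership of the analysis set is decided partly after allocation. In intervention clusters a child belongs to it only if vaccinated, and Protocol 5.4.2 makes that conditional: "If parents accept vaccination, the nurse will administer BCG and OPV". In control clusters the assigned treatment is standard care with information about vaccination, so there is no vaccine to decline. The receipt-of-treatment filter therefore acts mainly on one arm.

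Protocol 1.2 gives a reason to think about weight. In routine practice BCG is often delayed for infants below 2500 g, and "they are typically only vaccinated when they have reached 2500g". If some of that reluctance carried over to the home visit, small infants at higher risk would be lost mainly from the intervention side. The hazard ratio would then move in favour of vaccination without any vaccine effect. A weight term would remove the part of such selection that acts through weight.

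**Working it through.** **1. Information available, from the plan's own figures.** Protocol 5.3 gives 2.4% composite events, a design effect of 1.35, a 40% reduction, 80% power and 6666 children. Schoenfeld's formula with two-sided alpha 0.05 gives 4 × (1.960 + 0.842)² / (ln 0.6)² = 120.3 events. Then 120.3 / 0.024 × 1.35 = 6768, or 6806 with 121 events. Both are within about 2% of 6666, provided 2.4% is read as the average over both arms. This point disputes no figure in the plan.

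Effective composite events: 6666 × 0.024 / 1.35 = 118.5. SE of the log HR: 2 / √118.5 = 0.184.

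**2. Chance imbalance and precision.** Inputs from the documents: 6666 children and 55 + 37 = 92 clusters, so about 72 children per cluster. Assumed, not in the documents: an intracluster correlation (ICC) of weight of 0.01 to 0.05, and a log HR of 0.5 to 0.7 per SD of weight.

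SD of the standardised weight difference between arms = √[4/6666 × (1 + 71 × ICC)].

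- ICC 0.01: √(0.00060 × 1.71) = 0.032. Times 0.5, the shift in log HR is 0.016.
- ICC 0.05: √(0.00060 × 4.55) = 0.052. Times 0.7, the shift is 0.037.

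A one-SD imbalance thus moves the HR by about 1.6 to 3.7%, or 0.09 to 0.20 of one standard error. Squared, these ratios are 0.8% and 4.0% of the variance at the two extremes. A gain of about 1 to 2% is a reasonable central figure. It is smaller for deaths alone, which are fewer than composite events. Imbalance and precision gain are the same quantity seen twice and should not be added.

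**3. Selection through weight, with a true HR of 1.** Assumed: share q below 2500 g of 10 to 15%; mortality ratio R of 3 to 5; fraction f of small intervention infants leaving the set unvaccinated; no other losses.

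Apparent HR = {[q(1 − f)R + 1 − q] / (1 − qf)} / (qR + 1 − q).

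Worked case, q = 0.15, R = 5, f = 0.20: numerator (0.60 + 0.85) / 0.97 = 1.495; denominator 0.75 + 0.85 = 1.60; HR = 0.934.

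| f | q = 0.10, R = 3 | q = 0.10, R = 5 | q = 0.15, R = 3 | q = 0.15, R = 5 |
|---|---|---|---|---|
| 10% | 0.985 | 0.974 | 0.980 | 0.968 |
| 20% | 0.969 | 0.948 | 0.960 | 0.934 |
| 40% | 0.938 | 0.893 | 0.917 | 0.864 |

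The ranges are 0.97-0.98, 0.93-0.97 and 0.86-0.94. If leaving depends on weight alone, a model with weight correctly specified returns 1.00 in every cell.

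**4. Effect on the test.** Take q = 0.15 and R = 5, and let 2% of normal-weight intervention infants also leave. With f = 10, 20 or 50% the apparent HR is 0.97, 0.94 or 0.83. With the SE of 0.184, the two-sided rejection rate is 5.2, 6.3 or 17.1% instead of 5%. These rates are for the composite; inflation is smaller for deaths.

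**5. What weight cannot remove.** Suppose 10% of small intervention infants leave and their mortality is twice the average for small infants. The HR among small infants is then (1 − 0.10 × 2) / (1 − 0.10) = 0.89, even after adjustment for weight.

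**The case against.** A reader might infer that small infants are in fact being dropped from the intervention arm. The documents do not support that. Protocol 1.2 describes routine services. The trial nurse tells parents in intervention clusters that vaccination at birth is recommended and applies no weight limit; none appears in Protocol 5.4.4, Protocol 5.4.5 or SAP Table 2. Low-birthweight infants are expected in the analysis, since they form a planned subgroup. Consent is sought in pregnancy and reconfirmed before allocation is revealed (Protocol 5.4.1 and 8.2), so some families who would refuse leave both arms alike. The moribund and already-vaccinated exclusions also apply to both arms. Losses of 20 or 40% have no support in the text.

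A reader might also take the SAP's word unadjusted to mean no baseline information at all. It does not: the model is stratified by sex, region and pre-study mortality level. Nor is chance imbalance a bias; it is random error, already covered by the cluster-robust interval.

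Part of any selection would also be visible under the current plan, through exclusion reasons by arm, weight by arm, effects by birthweight group and an intention-to-treat analysis.

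All of this stands, and it limits the size of the point. It does not remove it. Table 5 estimates effect modification and gives no overall adjusted effect. Intention-to-treat is a sensitivity analysis. Neither carries the conclusion, and the receipt-of-treatment filter still falls mainly on intervention clusters.

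**Conclusion.** The point holds as a modest, inexpensive improvement. The model that carries the conclusion omits a collected baseline variable whose close relative, birthweight, the SAP itself describes as prognostic. The sure benefit is small: about 1 to 2% in variance, on assumed ICC and prognostic strength. The conditional benefit is protection against the weight-related part of any selection in the per-protocol set. On the assumptions in step 3, that is worth 2 to 3% in the HR if 10% of small intervention infants are lost and 6 to 14% if 40% are lost, against a planned effect of 0.60. The share of small infants, their mortality ratio and the loss fraction are all assumptions, and the documents do not establish that any such loss happens. The direction, if it does, favours the intervention. Adjustment would not deal with frailty within weight groups.

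**What to change.** In SAP Tables 2 and 8, add weight at enrolment as a covariate to the stratified Cox model and pre-specify three things:

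- the functional form, for example continuous with linear and quadratic terms;
- a rule that keeps children with a missing weight in the analysis, since the complete-case rule in SAP Appendix 1, section 4 would otherwise drop them;
- reporting of the model without weight alongside.

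Amend the sentence in SAP Appendix 1, section 2 on which analysis carries the conclusion so that it agrees.

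The cost is SAP wording and one covariate already collected; the sample size does not change. The downside is that the functional form and the missing-weight rule must be fixed in advance. The SAP should also say that this adjustment does not replace the intention-to-treat comparison, the only planned analysis that restores the children lost through the receipt-of-treatment rule.

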further investigated via the *stcox* procedure and the *tvc()* option. For the models including effect modifications we will construct a new interaction variable (i.e., a four-level variable representing the interaction) such that a graphical assessment of proportionality can be undertaken assessing the four-level variable in a log-log survival plot.

If we identify evidence for non-proportionality, we will still report the marginal hazard ratios but supplement this measure by hazard ratios for 2-3 properly selected categorical time-periods identified based on the aforementioned proportionality investigations.

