Statistical tool	Cox proportional hazards model
Stratification	We will employ models that allow for different baseline hazards according to sex, region and pre-study mortality level
Clustering	We will use robust standard errors to account for clustering within village cluster
Outline stata code For analysis: For model checking:	<pre> stset outdate, f(dead==1) enter (max(dob+1, date_enrol) /// exit (min (dnasc+60, date_mobileteam) origin(dob) stcox random, strata(sex reg prmorlev) vce(cl regam) estat phtest, detail† stphplot, strata(random) adj(sex reg prmorlev) stcox random, strata(sex reg prmorlev) vce(cl regam) tvc(random) texp(_t) *reg=region, prmorlev=pre-study mortality level, regam=village cluster </pre>

† If the proportional hazards assumption is not fulfilled we will still report the marginal hazard ratio but it will be supplemented by hazard ratios for two-three categorized time periods.

3 Effect-modifier analyses of primary outcome

We will assess whether the effect of the intervention on the primary effect measure is modified by the following potential effect modifiers.

Table 3. Sex as a potential effect modifier of the primary outcome

Potential effect modifier	Sex
Design	We will perform the analysis as describe above (for the primary analysis) allowing the effect of the intervention to differ between the sexes.
Reasoning	Previous studies have found sex-differential non-specific effects ^{1 2} , therefore, we will assess the sex-differential effects.
Outline stata code: For analysis: For model checking:	<pre>stcox random#sex sex, strata(sex reg pmorlev) vce(cl regam) contrast random#sex estat phtest, detail† stphplot, strata(random_sex) adj(sex reg pmorlev) stcox random#sex sex, strata(sex reg pmorlev) vce(cl regam) /// tvc(random#sex sex) texp(_t) *reg=region, pmorlev=pre-study mortality level, regam=village cluster, random_sex=a four-level variable based on the four possible combinations of random and sex</pre>

† If the proportional hazards assumption is not fulfilled we will still report the marginal hazard ratio but it will be supplemented by hazard ratios for two-three categorized time periods.

Table 4. Maternal BCG scar as a potential effect modifier of the primary outcome

Potential effect modifier	Maternal BCG scar (yes/no)
Design	We will perform the analysis as described above (for the primary analysis) allowing the effect of the intervention to differ by maternal BCG-scar status

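### If proportional hazards fail, the SAP takes the reporting periods from the same checks that show the failure, so the supplementary period-specific hazard ratios will tend to be exaggerated

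*SAP*

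**What the plan says.** SAP Appendix 1, section 5 sets out three checks on the trial's own data. First, "we will perform formal significance tests based on Schoenfeld residuals". Second, the model is refitted "allowing the hazard ratio to interact with the underlying timescale to identify a possible time trend". Third, "we will assess proportionality graphically via log-log survival curves".

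A positive finding leaves the overall estimate in the report and adds to it "hazard ratios for 2-3 properly selected categorical time-periods identified based on the aforementioned proportionality investigations".

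Appendix 2 repeats the rule as a footnote under Tables 2 to 8 and Table 13: the marginal hazard ratio will be "supplemented by hazard ratios for two-three categorized time periods". Those tables cover the primary outcome, its four effect modifiers, admissions, the composite and cause-specific death. Section 4 of that appendix extends the four modifiers to the composite.

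On significance, Appendix 1, section 1 applies two-sided p≤0.05 to analyses involving the primary outcome. Section 3 says "P-values will not be corrected for multiple testing", and sets no significance threshold for secondary outcomes or sensitivity analyses.

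**The concern.** Each check shows how the contrast between the arms changes with age. Cut-points drawn from them follow that contrast, including its noise, and the hazard ratios are then estimated in those periods from the same events. This is one source of exaggeration. The second is that the periods are reported only when the data already look non-proportional. The ordinary confidence intervals allow for neither.

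It matters here because the background invites an early-period claim. Protocol 1.2 reports that the effect of BCG on neonatal mortality "was seen already during the first three days post-vaccination", with a 58% reduction (8 to 81%). Protocol 5.5.1 concedes that mortality may not give a conclusive result. If the marginal result is inconclusive, a striking hazard ratio in an early period chosen from the data is the finding most likely to be highlighted.

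**Working it through.** **The plan's own figures.** The rule on periods carries no number. The nearest figures are in Protocol 5.3: 6666 children, 2.4% with the composite event, a 40% reduction, 80% power and design effect 1.35. The Schoenfeld formula at two-sided 5% needs 121 events for a hazard ratio of 0.6. Then 121 × 1.35 / 0.024 = 6806, which is 2.1% above 6666 if 2.4% is the overall proportion. These figures serve only to bracket event counts:
- composite events with no effect: 6666 × 0.024 = 160;
- composite events at hazard ratio 0.6 with 2.4% in controls: 6666 × 0.0192 = 128;
- deaths: not given in the documents, so 60 to 160 events is an assumed range.

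**Simulation.** There were 12,000 trials per scenario. Each event falls in the intervention arm with probability HR/(1+HR). Half the events are assumed to fall in days 1 to 7, and clustering is ignored. The trigger is a Schoenfeld-type test of arm by age at two-sided 5%. The data-driven rule takes the single cut, from 15 candidate ages between days 3 and 45, that best separates the two period hazard ratios.

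**No true effect, SAP-style rule (trigger, then best-separating cut).**

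| Events | Trigger positive | Of these, some period p≤0.05 | Product, per model | Mean lower period HR (truth 1.0) |
|---|---|---|---|---|
| 60 | 5.2% | 87.7% | 4.6% | 0.46 |
| 100 | 5.0% | 88.1% | 4.4% | 0.53 |
| 160 | 4.5% | 91.1% | 4.1% | 0.57 |

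A separate run at 80 and 120 assumed deaths gave about 4% per model, about 80% of triggered trials, and a mean lower hazard ratio of 0.52 to 0.57.

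**Benchmark: one fixed cut (day 7 or 28), reported in every trial.** Some period has p≤0.05 in 9.4 to 10.6% of null trials (theory: 1 − 0.95² = 9.75%). The lower hazard ratio averages 0.80 to 0.88, which is below 1 only because it is the lower of two.

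**Fixing the cut but keeping the trigger.** Among triggered null trials, 43 to 57% still show a period with p≤0.05. Conditional reporting is therefore a source of exaggeration in its own right.

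**Genuine non-proportionality.** The table gives the lower period hazard ratio as a multiple of its true value.

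| Truth | Events | Trigger + best cut | Trigger + day-7 cut | Day-7 cut, always reported |
|---|---|---|---|---|
| HR 0.6 to day 14, then 1.0 | 60 | 0.59 | 0.68 | 0.87 |
| HR 0.6 to day 14, then 1.0 | 128 | 0.72 | 0.81 | 0.94 |
| HR 0.42 to day 7, then 1.0 | 60 | 0.60 | 0.71 | 0.94 |
| HR 0.42 to day 7, then 1.0 | 128 | 0.76 | 0.86 | 0.99 |

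The exaggeration shrinks with more events and with stronger true non-proportionality. It did not vanish in any scenario. In the last two rows the fixed cut coincides with the true change point, which flatters it.

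**The case against.** The strongest reply is that the rule is conditional and supplementary. Several stronger readings are tempting, and the documents do not support them.

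- **A false-positive rate near 30%.** Splitting every null trial at its best-separating cut gives a period with p≤0.05 in about 30% of trials. The SAP splits only on evidence of non-proportionality, and with a 5% trigger the rate is about 4% per model. What remains is that the SAP states no trigger level and uses three checks, one of them graphical. A looser trigger would raise the rate, up to about 30% for a single cut with no trigger at all.
- **The SAP tells analysts to maximise the contrast.** It does not; it asks only for a proper selection. The best-separating cut is therefore near the upper end of what the rule allows.
- **The main result is at risk.** It is not. The marginal hazard ratio is always reported and the rule does not alter it.
- **Significance is inflated in every table.** The threshold covers only the primary outcome, including its effect-modifier tables. For admissions, the composite and cause-specific death the SAP sets none, so the harm there is exaggerated estimates only. The SAP also promises hazard ratios by period and does not mention p-values for them.
- **Fixed periods would remove the problem.** Three fixed periods reported in every trial still give some p<0.05 in 11 to 14% of null trials (theory: 1 − 0.95³ = 14.3%). They must be read descriptively.

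The reply limits the size of the point. It does not answer the exaggeration once a trigger has occurred.

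**Conclusion.** The point holds in a limited form and is minor. When the rule is triggered, period-specific hazard ratios will on average be too far from each other and their nominal intervals too narrow, although not in every dataset.

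In a null trial that triggers, some period reaches p<0.05 in about 80 to 90% of cases, where two independent tests would nominally give 9.75%. Under real non-proportionality, the lower period hazard ratio after a trigger averaged 0.59 to 0.76 of its true value.

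These sizes rest on assumed event counts, a 5% trigger, the best-separating single cut, half the events in the first week, and no clustering. The direction does not depend on the exact values. It follows from using the same data to choose and to estimate, and from reporting only after a positive check.

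**What to change.** Before any outcome is analysed by arm, add to SAP Appendix 1, section 5:

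1. Two or three age periods chosen on the sponsor's own rationale, for example with a cut at 28 days. An early cut needs care. Protocol 1.2 speaks of days after vaccination, whereas the model runs on age and children may enter up to 72 hours after birth. A child vaccinated near 72 hours contributes almost nothing to days 1 to 3 of age.
2. Report the period hazard ratios for the primary outcome, and for the composite if events allow, whatever the proportionality tests show. Present them as descriptive supplements without significance claims.
3. Label any split chosen from the data as exploratory.

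Fixing the cuts and dropping the trigger are both needed, because fixed cuts reported only after a positive test remain exaggerated.

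The cost is a sentence or two in the SAP and the corresponding footnotes. Fixed periods may fit an unexpected pattern less well. They may also be too sparse in the effect-modifier and cause-specific tables, where they can be omitted.
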